17.3.2 PK analysis set

The PK analysis set (PKAS) will consist of all subjects who received at least one dose of study IP and provided at least one full set of PK plasma sampling and no major deviation judged to compromize the PK analysis. Individual PK values and/or full profiles for explicit IPs may be excluded from the analysis as specified in the SAP.

17.3.3 Additional analysis datasets

Additional datasets may be created as needed for exploratory analyses.

17.4 Description of study population

17.4.1 Demographics and baseline characteristics

Demographics, weight and height will be presented by treatment through descriptive statistics.

17.4.2 Medical/surgical history and prior/concomitant medication

Medical/surgical history will be presented by treatment by system organ classes (SOC) and preferred term (PT) and Prior/concomitant medications will be presented by treatment by ATC level 1, 3 and 5 through descriptive statistics and listings.

17.4.3 *History of nicotine use*

History of snus use and smoking will be presented through descriptive statistics.

17.4.4 *Treatment compliance*

The number of subjects treated with each treatment will be presented through descriptive statistics and listings.

17.4.5 Physical examination

Abnormal findings will be specified and presented by subject and summarized by treatment and period through descriptive statistics.

17.5 Analysis of primary endpoints

17.5.1 Comparison of nicotine exposure after administration of ZYN Moist 7 mg and Longhorn 18 mg

The PK analysis will be based on the PK analysis set and performed by CTC. The PK parameter will be calculated by non-compartmental analysis (NCA) using the software Phoenix WinNonlin[®] version 8.1 or later (Certara Inc, Princeton, New Jersey, U.S.A.).

 AUC_{inf} based on plasma concentrations of nicotine after administration of one single dose of ZYN Moist 7 mg of nicotine will be compared to that of a single dose of Longhorn 18 mg and be described using summary statistics Student's t-test for between treatment difference. For details on calculation of AUC_{inf} , see Section 17.6.1.

17.6 Analysis of secondary endpoints

17.6.1 Analysis of pharmacokinetics

The PK analysis will be based on the PK analysis set and performed by CTC. The PK parameters will be calculated by NCA using the software Phoenix WinNonlin[®] version 8.1 or later (Certara Inc, Princeton, New Jersey, U.S.A.).

The following non-compartmental PK parameters will be determined for each IP treatment:

- T_{max} (sampling time at which C_{max} occurred)
- C_{max} (maximum observed concentration)
- AUC_{inf} (area under the plasma concentration-time curve from time 0 to infinity)
- AUC_{0-1.5h} (area under the plasma concentration-time curve from time 0 to 1.5 hours)
- $T_{\frac{1}{2}}$ (terminal elimination half-life)

 C_{max} and T_{max} will be derived from the observed plasma concentration data. The AUC will be calculated using log-linear trapezoidal interpolation. Calculations will be based on the actual sampling times recorded during the study. Concentrations below Lower limit of quantification (LLOQ) occurring before C_{max} will be treated as zero. Concentrations below LLOQ occurring after C_{max} will be omitted from the analysis. AUC_{inf}, AUC_{0-1.5h}, and C_{max} will be corrected for nicotine baseline concentrations.

Pharmacokinetic data will be summarized for each IP treatment using summary statistics. Data will be presented in terms of N, arithmetic mean, SD, minimum and maximum value. In addition, for the parameters AUC and C_{max} the geometric mean and CV will be presented. Between-treatment differences for all pairwise comparisons will be analyzed using signed Student's t-test. Categorical data will be presented as counts and percentages as applicable.

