7.2 Secondary objectives

The secondary objectives are:

- 1. To compare the pharmacokinetic profile of each of the non-tobacco-based nicotine pouches and Longhorn 18 mg.
- To compare the estimated in vivo extracted amount (mg/unit) and extracted fraction (%) of nicotine from each product.
- 3. To correlate the estimates of pharmacokinetic (PK) parameters and the total amount of nicotine extracted from each product.
- 4. To evaluate the subjective effect on urge to snus for all products

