7.2.1 Secondary endpoints

The secondary endpoints are:

- 1. Pharmacokinetics of nicotine in plasma: The difference in T_{max}, C_{max}, AUC_{inf}, AUC_{01.5h} and terminal elimination half-life of the non-tobacco-based nicotine ZYN Moist pouches, ZYN Dry Mini pouches and Longhorn 18 mg.
- 2. The difference in in vivo extracted amount of nicotine (mg/unit) and extracted fraction (%) from all products.
- 3. Correlation between total extracted amount of nicotine and C_{max} and AUC_{inf} .
- 4. The difference in the urge to snus, measured using a 100-mm visual analogue scale (VAS) anchored with "not at all" to "extremely" at pre-set time points up to 60 minutes after start of the investigational product (IP) administration will be compared among the products.

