8 STUDY DESIGN

8.1 Overall study design and schedule of events

This is an open, randomized, six-way cross-over, single dose administration study designed to assess the pharmacokinetic profile of non-tobacco-based nicotine pouches and tobacco-based US moist snuff pouches. The study will include 36 subjects.

The subjects will come for 6 treatment visits to the clinic, in addition to a visit for screening and a follow-up (FU) telephone visit. Screening (Visit 1) will take place from Day -28 to Day -1 and will include an eligibility check including evaluations of smoking and snus use, medical history and collection of height and weight, see Table 8.1-1 for details. Between each treatment visit a wash-out period of at least 24 hours is required.

Subjects shall be abstinent from snus and all other nicotine containing products for at least 12 hours before treatment and are instructed to abstain from snus or other nicotine delivery products as from 8.00 p.m. the evening before and to refrain from smoking 24 hours before each treatment visit. All IP administrations are performed during the morning hours to facilitate abstinence. The subjects should certify abstinence before each treatment is started.

The IPs are administered as single doses in a pre-determined randomized order. The subject keeps the pouch still between the upper lip and the gum for 60 minutes and are instructed not to manipulate the pouch with the tongue or lips. The subjects are instructed not to eat, drink, chew chewing gum or brush teeth from 30 minutes before application of the IP, during application of the IP and 30 minutes after the IP has been taken out [3].

After 60 minutes the pouches are collected and frozen (-20°C) pending analysis of residual nicotine content.

Blood samples for assessment of plasma levels of nicotine will be collected at pre-defined time points from pre-dose to 6 hours after IP administration, see Table 8.1-2 for detailed sampling schedule. In addition, urge to snus (using VAS) and pharmacodynamic effect of nicotine (by measuring pulse rate) will be determined, see Table 8.1-2.

Study assessments are described in Section 11.

Table 8.1-1Schedule of events

Visit	Visit 1 Screening	Visit 2-7 (Cross-over)	Visit 8 Telephone FU
Assessments / Study days	-28 to -1		7 days (-3/+7) after last dose
Informed consent	X		
Demographics	X		
Medical/surgical history	X		
History of nicotine use	X		
Inclusion/exclusion criteria	X	X ¹	
Physical examination	X		
Weight, height	X		

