11.3 Assessments related to primary endpoints

11.3.1 Pharmacokinetic sampling and analysis

Venous blood samples (approximately 5 mL) for the determination of plasma concentrations of nicotine after administration of the IP, will be collected through an indwelling venous catheter at pre-specified time-points; pre-dose (within 15 min prior to dose), 5 min, 10 min, 15 min, 30 min, 45 min, 1h, 1h:15 min, 1h:30 min, 2h, 4h, 6h post-dose, see Table 8.1-2. Actual time for blood PK sampling must not deviate from the planned time more than:

 \pm 2 minute for time-points up to 30 minutes post-dose.

 \pm 5 minutes for time-points up to 90 minutes post-dose.

 \pm 10 minutes for time-points up to 6 hours post-dose.

Pre-dose sampling may be performed within 15 minutes prior to dosing.

The date and time of collection of each sample will be recorded in the eCRF.

The blood samples will be collected in pre-labelled tubes. All the collected blood samples will be centrifuged to separate plasma. The separated plasma from each blood sample will be divided into 2 aliquots in pre-labelled cryotubes and frozen at -20°C.

For further details see lab manual.

Plasma samples for determination of plasma concentrations of nicotine will be analyzed by Lablytica by means of a validated using LC-MS/MS method. Samples from all evaluable subjects will be analyzed.

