17.1 General

Continuous data will be presented with descriptive statistics in terms of evaluable and missing observations, arithmetic mean, standard deviation (SD), median, minimum and maximum value, Q1-Q3 (interquartile range [IQR]). In addition, for the parameters AUC and C_{max} the geometric mean and coefficient of variation (CV) will be presented.

Categorical data will be presented as counts and percentages. When applicable, summary data will be presented by treatment, and by assessment time. Individual subject data will be listed by subject number, treatment, and, where applicable, by assessment time.

All descriptive summaries and statistical analyses will be performed using SAS Version 9.4 or later (SAS Institute, Inc., Cary, NC).

Baseline will be defined as the visit with last data collection point prior to the first administration of IP.

All hypothesis testing will use a significance level of 5%.

No imputation of missing data will be performed.

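### Section 17.6.1 fixes a Student's t-test for Tmax, a sampling time on a coarse, uneven grid; a paired rank analysis suits it better and should have more power

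*Protocol*

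**What the plan says.** Section 17.6.1 opens its list with "The following non-compartmental PK parameters will be determined for each IP treatment" and names Tmax, Cmax, AUCinf, AUC0-1.5h and terminal half-life. Tmax is defined there as the "sampling time at which C_{max} occurred". The test rule that follows exempts no parameter: "Between-treatment differences for all pairwise comparisons will be analyzed using signed Student's t-test". Unlike the sections on correlation, urge to snus and pulse rate, this sentence does not hand the choice to the SAP.

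Section 11.3.1 sets the schedule: pre-dose, then "5 min, 10 min, 15 min, 30 min, 45 min, 1h, 1h:15 min, 1h:30 min, 2h, 4h, 6h post-dose".

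The PK summary list in section 17.6.1 gives N, arithmetic mean, SD, minimum and maximum but not the median, although the general list in section 17.1 includes the median and quartiles. Section 17.6.2 already plans a signed Wilcoxon test on within-subject differences for the extracted dose.

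On scope, secondary objective 1 is "To compare the pharmacokinetic profile of each of the non-tobacco-based nicotine pouches and Longhorn 18 mg". Secondary endpoint 1 refers to differences in the same five parameters, ending with "terminal elimination half-life of the non-tobacco-based nicotine ZYN Moist pouches, ZYN Dry Mini pouches and Longhorn 18 mg", which is not limited to comparisons with Longhorn. Section 17.1 adds "All hypothesis testing will use a significance level of 5" per cent.

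**The concern.** A t-test compares means, and a mean is a natural summary when the scale is continuous and roughly symmetric. Tmax here is neither. Apart from small deviations between actual and planned times, it takes one of 11 values. A peak that falls between 2 h and 4 h can only be recorded at one end of a two-hour gap, whereas an early peak is located to within 5 minutes. The size of a mean difference is thus partly a product of where the samples were placed, and a few late values weigh heavily on both the mean and the SD.

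At stake is the plan's ability to show whether the pouches differ from Longhorn in speed of uptake, one of the features that secondary objective 1 sets out to compare. An insensitive test could leave a real difference unseen. The summary list for the same section would not show the median that a reader needs to interpret Tmax.

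**Working it through.** **Inputs.** Five PK parameters and the t-test rule: section 17.6.1. Eleven post-dose times: section 11.3.1. Six products: section 8.1 ("This is an open, randomized, six-way cross-over, single dose administration study"). Alpha 0.05: section 17.1, taken as two-sided because the sidedness is not stated. Evaluable subjects: 32, section 17.2. The name of the t-test in section 17.6.1 is not standard; I read it as paired.

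**The plan's own figure.** 32 / (1 − 0.10) = 35.6, rounded up to 36 randomized. This reproduces section 17.2, so n = 32 is used below. The protocol gives no power, effect size or SD for any parameter.

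**Weight of one late value.** If one subject's Tmax is recorded at 240 min instead of 60 min, the mean paired difference moves by (240 − 60) / 32 = 5.6 min.

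**Can late values alone create significance?** Let k of 32 differences equal c and the rest be zero.
- k = 1: mean = c/32; variance = (c² − c²/32)/31 = c²/32; standard error = c/32; t = 1.00.
- k = 2: mean = 0.0625c; variance = (2c² − 4c²/32)/31 = 0.0605c²; standard error = 0.0435c; t = 1.44.

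Both are below the critical value of 2.04 on 31 degrees of freedom, whatever the size of c, because the same values inflate the SD.

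**Simulation on the sampling grid.** 4,000 runs per scenario, n = 32, nominal times, the two products drawn independently within a subject. The Tmax distributions are assumptions, since the documents give none (percentages):

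| Product | 15 min | 30 min | 45 min | 60 min | 75 min | 90 min | 2 h | 4 h |
|---|---|---|---|---|---|---|---|---|
| A, comparator | 1 | 4 | 15 | 50 | 20 | 7 | 2 | 1 |
| A, earlier | 3 | 12 | 27 | 40 | 10 | 4 | 2 | 2 |
| B, comparator | 1 | 4 | 15 | 50 | 20 | 5 | 2 | 3 |
| B, earlier | 3 | 12 | 27 | 40 | 10 | 3 | 2 | 3 |

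| Scenario | Paired t | Signed-rank |
|---|---|---|
| A, both products as comparator (type I error) | 0.037 | 0.047 |
| B, both products as comparator (type I error) | 0.029 | 0.044 |
| A, earlier against comparator (power) | 0.219 | 0.325 |
| B, earlier against comparator (power) | 0.183 | 0.325 |

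About 32% of paired differences were exactly zero in the null scenarios and 27% in the shifted ones. Both tests hold the 5% level, and the t-test falls below it. The signed-rank test gains about 0.11 to 0.14 in power.

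**Scope of the comparisons.** Six products give 6 × 5 / 2 = 15 pairs, hence 15 × 5 = 75 tests over five parameters. Secondary objective 1 implies 5 pairs, hence 5 × 5 = 25 tests. Like for like, the ratio is three to one. Section 17.7.3 sends AUC0-30min through the same rule, which adds 15 more tests.

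**The case against.** Tmax is one secondary parameter, and at n = 32 a paired t-test is fairly robust. A 4 h peak is hypothetical: the pouch is removed at 60 minutes and nothing in the protocol suggests peaks that late. Section 17.1 already plans the median and quartiles for continuous data in general, and technical detail is left to a SAP that is not at hand. The power figures rest on invented distributions.

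Much of this stands. It limits the point to suitability and power, and the exact size is uncertain. It does not remove the point, because section 17.6.1 states the test outright and a SAP that follows it inherits the choice.

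Two stronger readings are tempting, and the documents support neither.

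- *One or two late profiles could produce a spurious Tmax difference.* The algebra above shows that on their own they cannot, and the simulated error rate is below 5%. Such profiles can mask a difference.
- *Seventy-five unadjusted tests put the trial's error rate out of control.* Under a global null, 75 × 0.05 = 3.75 false positives would be expected. That null requires six products containing 3 to 18 mg of nicotine to be identical on all five parameters. These tests are secondary, the single primary comparison keeps its own error rate, and whether to adjust secondary PK tests is a matter of judgement that a SAP may settle. Nor are ZYN-versus-ZYN comparisons plainly unasked for, given the wider wording of secondary endpoint 1.

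**Conclusion.** The point holds for Tmax. The t-test that section 17.6.1 fixes is poorly suited to a tied, unevenly spaced sampling time. Under the assumed distributions it is conservative and has power of about 0.2, against about 0.33 for the signed-rank test. The direction of that result is credible whenever a few late values are present; its size depends on Tmax distributions that the documents do not give, on nominal times and on independent draws within a subject. No inflation of type I error is shown, and the primary AUCinf analysis is not affected.

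The scope of the pairwise testing is a secondary remark only: the analysis covers 15 pairs, secondary objective 1 names five, and secondary endpoint 1 can be read either way. This is wording to reconcile, not a demonstrated error.

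**What to change.** In section 17.6.1, take Tmax out of the t-test rule. Analyse it with the paired Wilcoxon signed-rank test, the kind of test that section 17.6.2 already plans for extracted dose, and report the Hodges-Lehmann median difference with a confidence interval. Add the median to that section's summary of Tmax. Replace the non-standard name of the t-test with the one intended, presumably the paired t-test, for the other parameters.

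Align sections 7.2, 7.2.1 and 17.6.1 on which product pairs are to be compared. If the objective governs, keep formal tests to the five comparisons with Longhorn and present the ten ZYN-versus-ZYN pairs as descriptive estimates. If any adjustment is adopted for secondary comparisons, leave the primary AUCinf comparison of ZYN Moist 7 mg with Longhorn outside it.

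The cost is protocol and SAP wording and standard SAS procedures, with no new data, visits or subjects. If the objective governs, formal p-values for the ZYN-versus-ZYN pairs are given up.

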17.6.2 In vivo extracted amount of nicotine

The data needed for the analysis of in vivo extracted amount of nicotine are the individual data of amount of nicotine for unused reference pouches and the amount of nicotine left in the study pouches. The difference between the nicotine content of the reference pouch and the study pouch will be used to calculate the extracted amount. The mean of extracted amount (mg/unit) and extraction fraction (%) of nicotine for each IP pouch, will be calculated. The extracted dose of nicotine will be analyzed using the signed Wilcoxon rank sum test for within subject difference (i.e. between IPs). Amount of nicotine in reference pouches and in used pouches will be presented through descriptive statistics.

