Traditionally there has been no non-tobacco-based nicotine product intended for recreational use. Despite the vast risk differential between snus and cigarettes in terms of adverse long-term health effects, snus remains a controversial product as it contains tobacco, is intended for recreational use, and is potentially addictive. The tobacco component of snus explains why it contains measurable amounts of unwanted, potentially carcinogenic constituents, albeit at very low concentrations. Recently, a novel, non-tobacco-based nicotine product (ZYN) has been developed and is now commercially available. It has some features that are similar to snus since it comes in pouches that are intended to be placed under the upper lip. However, in contrast to snus, the product contains no nitrosamines or polycyclic hydrocarbons which are the two main classes of unwanted substances in snus. The nicotine content in ZYN is comparable to that in snus and many other oral tobacco products that are currently common on the market in Scandinavia and the U.S.

When comparing the nicotine content of different nicotine-delivery products it is important to consider that the nicotine extraction and uptake varies considerably depending on product type (tobacco versus a non-tobacco-based matrix) and product formulation (pouch geometry, water content, particle size, pH, etc). In addition, there is a substantial inter-individual variation in uptake with products used orally which is probably related to constitutional

differences in saliva production and results in a wide variation in nicotine extraction from the product.

Commercially available oral tobacco products in the Scandinavian and U.S market have a nicotine content ranging between 3 mg/unit and more than 20 mg/unit.

Previous studies [2], have indicated that on average about 15-20% of the total nicotine content is extracted and absorbed, although with large interindividual variation. Recent in-house data (Swedish Match) shows an extracted fraction of about 20 - 30% following a 1-hour exposure. Extraction is generally not linear with pouch size: it is larger with small compared to larger pouches, which suggests that surface area, saliva penetration and diffusion factors may be more important determinants of nicotine uptake than pouch weight.

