10 TREATMENTS

The IPs, both test- and reference products are supplied by Swedish Match AB.

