10.3 Manufacturing, packaging and labelling

The production sites and batch ID for the IP and reference product will be documented in trial master file.

The IP will be manufactured and packaged in compliance with the Swedish law on food production.

The IP will be transferred from the original container, weighed and individually packaged in identical sealed food approved test containers at the Swedish Match analytical lab.

The containers will be labelled with unique identification numbers by Swedish Match in accordance with the randomization list.

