17.6.3 Extracted nicotine versus nicotine exposure

Correlation between total extracted amount of nicotine and C_{max} and AUC_{inf} will be analyzed using correlation analysis as further described in the SAP.

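### Extracted nicotine is computed without the study pouch's own weight, which adds avoidable random error to secondary endpoints 2 and 3

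*Protocol*

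**What the plan says.** Section 17.6.2 of the protocol names the data needed for the extraction analysis: "individual data of amount of nicotine for unused reference pouches and the amount of nicotine left in the study pouches". It then gives the calculation: "The difference between the nicotine content of the reference pouch and the study pouch will be used to calculate the extracted amount". No pouch weight appears among the inputs or in the formula. I read the reference pouch here as an unused pouch of the same product, not as the comparator product.

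Section 10.3 describes the preparation of the products: "The IP will be transferred from the original container, weighed and individually packaged in identical sealed food approved test containers". The opening of section 10 applies the term IP to both arms of the comparison ("The IPs, both test- and reference products are supplied by"), so the weighing covers all six products. No use of the weight is stated.

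The result feeds secondary endpoint 2 (extracted amount and extracted fraction) and secondary endpoint 3, which section 17.6.3 describes: "Correlation between total extracted amount of nicotine and" Cmax and AUCinf. For endpoint 2 the extracted dose "will be analyzed using the signed Wilcoxon rank sum test for within subject difference".

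**The concern.** Extraction is obtained as a small difference between two larger quantities measured on two different pouches. Any amount by which the used pouch differed from the reference at the start goes straight into the answer. Section 6.1 reports an "extracted fraction of about 20 - 30% following a 1-hour exposure" from in-house data, and from earlier studies that "on average about 15-20% of the total nicotine content is extracted and absorbed". At such fractions, a modest relative deviation in content becomes a sizeable relative error in what was extracted.

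The loss is in precision. Subject-level extraction values are noisier than they need be, and so are the within-subject differences between products. Endpoint 3 suffers most, because there the individual value is the datum and averaging over subjects does not help: a weak correlation with Cmax or AUCinf could partly reflect pouch weight. The measurement that would remove most of this is already planned.

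**Working it through.** **Inputs from the protocol.** Contents per pouch: 3, 6, 7, 9, 11 and 18 mg (sections 10.1 and 10.2). Extracted fraction f: 0.20-0.30, with 0.15-0.20 from earlier studies (section 6.1). Evaluable subjects: 32 (section 17.2). The only related stated figure that can be checked is the inflation for drop-out: 32/0.90 = 35.6, rounded up to 36, which agrees. It supplies n and nothing more.

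**Assumptions, not in the protocol.** Pouch-weight CV of 2%, 5% or 8%; nicotine content proportional to weight; for the correlation, mean f = 0.25 and between-subject CV of f = 30%.

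**Error per pouch.** Let the reference content be C and the study pouch start at C + d.

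- True extracted amount: f(C + d).
- Residual: (1 - f)(C + d).
- Protocol's estimate: C - (1 - f)(C + d) = fC - (1 - f)d.
- Error: fC - (1 - f)d - fC - fd = -d.

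With w = d/C, the error relative to the expected extracted amount fC is w/f in size: 1/0.30 = 3.3-fold to 1/0.20 = 5-fold magnification, and 1/0.15 = 6.7-fold at the lowest cited fraction. If the extracted fraction is formed with C as denominator, its error is -(1 - f)w, so a 5% deviation moves it by 3.5 to 4.0 percentage points.

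**Size** (error SD = C x weight CV; share = weight CV / f):

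| Weight CV | 7 mg pouch | 18 mg pouch | Share of extracted amount, f = 0.30 to 0.20 |
|---|---|---|---|
| 2% | 0.14 mg | 0.36 mg | 7-10% |
| 5% | 0.35 mg | 0.90 mg | 17-25% |
| 8% | 0.56 mg | 1.44 mg | 27-40% |

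The mean extracted amounts are 1.4-2.1 mg (7 mg pouch) and 3.6-5.4 mg (18 mg pouch).

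**Effect on means.** The error averages to zero when C is the true product mean. At a 5% CV and n = 32 the SE contributed is 0.35/√32 = 0.06 mg and 0.90/√32 = 0.16 mg.

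**Effect on endpoint 3.** The deviation also enters the true amount, with opposite sign to its effect on the estimate. To first order, with s the SD of f and v the weight CV, and everything divided by C²:

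- Var(true) = s² + f²v²
- Var(computed) = s² + (1 - f)²v²
- Cov = s² - f(1 - f)v²

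At f = 0.25, s = 0.30 x 0.25 = 0.075 and v = 0.05: Cov = 0.005156, Var(true) = 0.005781, Var(computed) = 0.007031, so r = 0.005156/√(0.005781 x 0.007031) = 0.81. At v = 0.02, r = 0.00555/√(0.00565 x 0.00585) = 0.97. At v = 0.08, r = 0.004425/√(0.006025 x 0.009225) = 0.59. For f = 0.20 and v = 0.05 the formula gives 0.73, and a simulation with 400,000 draws gives the same.

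**Sensitivity at v = 0.05.** With a between-subject CV of 50%, s = 0.125 and r = 0.015156/√(0.015781 x 0.017031) = 0.92. If the six products are pooled (mean of C² = 620/6 = 103.33; variance of C = 103.33 - 81 = 22.33; between-product term 0.0625 x 22.33 = 1.396), r = (1.396 + 0.533)/√((1.396 + 0.597)(1.396 + 0.727)) = 0.94.

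**After weight scaling.** The weight term cancels. Only variation in mg/g remains: an assumed 2% CV leaves an error SD of 0.14 mg (7 mg pouch) or 0.36 mg (18 mg pouch).

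**The case against.** The strongest reply is that section 17 announces itself as the principal features and leaves technical detail to the SAP, which is not at hand. Section 17.6.2 does not say how many reference pouches there are or how their content is assigned to a study pouch, so a weight correction could be added there without contradiction. That is fair as to what may happen in practice. But section 17.6.2, unlike the next three analysis sections, does not hand its calculation to the SAP; it lists the inputs and states the difference. As written, the formula is not weight-corrected.

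The objections on size mostly stand. The weight CV is an assumption, and at 2% the effect is minor. Section 6.1 reports large variation between people and higher extraction from small pouches, both of which reduce the relative damage. The correlation method is left to the SAP, and pooling the products would attenuate less than the within-product figures suggest.

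A reader might also infer more than the protocol supports:

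- That product means or product contrasts are biased. They are not, provided the reference mean is accurate. A single reference pouch per product would shift every subject's value for that product by its own deviation, but no number of pouches is given.
- That impossible negative amounts would be common. At a 5% weight CV and 20-30% extraction, simulation with between-subject CVs of 30% and 50% gives at most 0.6% of values below zero.
- That the comparison would be run unpaired because the test name contains the words rank sum. The words signed and within subject already point to the paired test, so this is a slip in the name only.

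**Conclusion.** The point holds as a cheap improvement in precision. The formula lets each pouch's content deviation into the extracted amount one for one, and about 70-80% of the relative deviation into the extracted fraction. The 3.3- to 5-fold magnification rests on the protocol's own 20-30% extraction; everything beyond it rests on an assumed weight CV. Over 2% to 8% the error SD runs from 7-10% to 27-40% of the extracted amount. The within-product correlation of true with computed extraction runs from about 0.97 to 0.59 (0.81 at 5%), at mean f = 25% and a between-subject CV of 30%. Secondary endpoints 2 and 3 lose precision. The primary endpoint, AUCinf in plasma, does not use extraction and is untouched.

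**What to change.** In section 17.6.2 (and the SAP), define starting content as the recorded pre-use weight of the study pouch times the mean nicotine concentration (mg/g) of unused pouches of the same product and batch, which must be weighed too. Extracted amount is that starting content minus the measured residual, and the extracted fraction uses the same starting content as its denominator. State how many unused pouches per product and batch are assayed.

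As a wording correction only, name the test the Wilcoxon signed-rank test.

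The cost is small but not nil. Section 10.3 says only that pouches are weighed, so the weights must be recorded, linked to each container number and transferred for analysis. Variation in mg/g within a batch remains and cannot be removed this way.
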